6.8.6 Validation of the models

In the validation data, we will fit an imputation model to enable imputation of missing values for ethnicity, body mass index, alcohol and smoking status. We will carry out 5 imputations. We will apply the risk equations for males and females obtained from the derivation data to the validation data and calculate measures of performance.

As in previous studies⁴², we will calculate R² values (explained variation where higher values indicate a greater proportion of variation in survival time explained by the model ⁴³), D statistics⁴⁴ (a measure of discrimination which quantifies the separation in survival between patients with different levels of predicted risk where higher values indicate better discrimination), Brier scores, and Harrell's C statistics at 1, 2, 5 and 10 years and combine these across datasets using Rubin's rules. Harrell's C statistic⁴⁵ is a measure of discrimination (separation) which quantifies the extent to which those with earlier events have higher risk scores. Higher values of Harrell's C indicate better performance of the model for predicting

the relevant outcome. A value of 1 indicates that the model has perfect discrimination. A value of 0.5 indicates that the model discrimination is no better than chance.

We will calculate 95% confidence intervals for the performance statistics to allow comparisons with alternative models for the same outcome and across different subgroups.⁴⁶

We will assess calibration of the risk scores by comparing the mean predicted risks with the observed risks by tenth of predicted risk. The observed risks will be obtained using Kaplan-Meier estimates evaluated at 10 years, obtained for men and women.

We will also evaluate these performance measures in 6 pre-specified age groups (25-49; 50-59; 60-69; 70-79; 80+), and in people on long term PPIs.

We will also compare the risk prediction model with a simple algorithm based only on criteria such as age and number of electronic prescriptions of PPI/H2 blockers and consider the use of decision curve analysies.

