6.8.8 Development of risk categories

Since there is no currently accepted threshold for classifying high risk of oesophageal cancer, we will examine the distribution of predicted risks and calculate a series of centile values. For each centile threshold, we will calculate the sensitivity of the risk scores.

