6.8.9 Sample size

Sample size calculations for a risk prediction model aim to ensure precise estimation of model parameters whilst minimising potential overfitting. We have used the criteria of Riley et al.⁴⁷ o derive a minimum sample size of 312,616 men corresponding to 543,952 person-years of follow-up. The number of outcome events needed are 349 assuming up to 70 predictors, an event rate of 0.00064, mean follow up of 1.74 years; timepoint 10 years, a R² value of 0.002013. Similarly, a minimum sample size of 665,050 women corresponding to 1,157,1871 person-years of follow-up. The number of outcome events needed are 359 assuming up to 70 predictors, an event rate of 0.00031; mean follow up of 1.74 years; a R² value of 0.0009468. Hence a minimum sample of just over 1 million men and women would be needed in the derivation dataset.

Collins, et al⁴⁸ suggests externally validating a prognostic model requires at least 100 events and ideally, at least 200.

With over 35 million patients and at least 18,000 incident cases of oesophageal cancer on QResearch, we can confirm we have more than ample data both in the training and validation datasets. We will use all the relevant patients on the database to maximise the power and generalisability of the results. We will use STATA (version 16) for analyses. We will adhere to the TRIPOD statement for reporting⁴⁹.

6.8.10 Public and patient involvement.

Patients will be involved in setting the research question, the outcome measures, the design, implementation and dissemination of the study findings. Patient representatives will also advise on dissemination including the use of culturally appropriate lay summaries describing the research and its results.

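### Calibration is specified only by tenth of predicted risk, so for any high-risk threshold above the 90th centile an error in absolute risk within the selected group can be diluted or averaged out

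*Protocol*

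**What the plan says.** Protocol section 6.8.6 names one calibration comparison: "comparing the mean predicted risks with the observed risks by tenth of predicted risk". On the observed side: "The observed risks will be obtained using Kaplan-Meier estimates evaluated at 10 years, obtained for men and women". The next paragraph extends the performance measures: "We will also evaluate these performance measures in 6 pre-specified age groups (25-49; 50-59; 60-69; 70-79; 80+), and in people on long term PPIs". Brier scores are planned, and the authors will "consider the use of decision curve analysies". No calibration slope, smoothed curve or finer grouping of the upper tail is named.

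Section 6.8.8 leaves the threshold open: "Since there is no currently accepted threshold for classifying high risk of oesophageal cancer, we will examine the distribution of predicted risks". The only quantity promised at each centile is sensitivity.

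Section 5 foresees sharing risk information in consultations, recalling patients according to their level of risk, and feeding mathematical models of the pathway. Section 6.8.5 puts the focus on 10-year risk estimates, and section 6.9.4 lists displays of absolute risk among the possible outputs.

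**The concern.** Calibration is examined on ten equal groups, selection is examined on centiles, and nothing joins the two. Sensitivity above a centile says what share of cases is captured. It does not say whether a person told that their 10-year risk is 5% really has a risk near 5%.

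For a rare cancer with strong risk factors, and with Barrett's patients kept in the cohort (section 6.2.3), the top tenth is likely to be very mixed. One average over it can look acceptable while risks near its upper end are too high, or those near its lower end too low. If the threshold lies in that range, the absolute risks quoted to patients and used in pathway modelling would rest on a check that was not made for those patients.

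**Working it through.** **The plan's own figures.** The calibration text gives no number, so the check starts from the sample size in section 6.8.9. The formula is n = P / ((S - 1) ln(1 - R²/S)), with P = 70 and S = 0.9 (S is assumed; it is not stated).

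- Men, R² 0.002013: n = 312,616. Person-years: 312,616 x 1.74 = 543,952. Events: 543,952 x 0.00064 = 348.1, rounded up to 349.
- Women, R² 0.0009468: n = 665,050. Person-years: 1,157,187 (the printed figure carries an extra digit). Events: 1,157,187 x 0.00031 = 358.7, rounded up to 359.

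The figures reproduce, which confirms that the event rates are per person-year.

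**Average 10-year risk.** 1 - exp(-10 x 0.00064) = 0.64% in men; 1 - exp(-10 x 0.00031) = 0.31% in women.

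**Spread of risk (assumed).** The protocol gives neither a C statistic nor a risk distribution. Take risk = 1 - exp(-exp(a + s z)), z standard normal, with the mean fixed at the male value.

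| | s = 1.25 (C about 0.81) | s = 1.5 (C about 0.85-0.86) |
|---|---|---|
| Risk at 90th centile | 1.46% | 1.45% |
| Risk at 99th centile | 5.29% | 6.74% |
| Share of cases in top 10% | 48.1% | 57.6% |
| Share of cases in top 1% | 13.5% | 19.0% |
| Top 1% as a share of the top tenth's cases | 0.280 | 0.330 |

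**Dilution.** Let predicted risk be 1.3 times true risk in the top 1% and correct elsewhere. Observed/expected in the top 1% is 1/1.3 = 0.77. For the whole top tenth it is 1 - w(1 - 1/1.3), where w is the last row of the table:

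- w = 0.280: 1 - 0.280 x 0.231 = 0.935
- w = 0.330: 1 - 0.330 x 0.231 = 0.924

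A 23% shortfall in the top 1% therefore appears as 6-8% in the tenth and is hard to tell from a small uniform error. For the tenth to read exactly 1.00, the rest of it would need observed/expected of (1 - w/1.3)/(1 - w), which is 1.09 to 1.11.

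**A broader error is visible.** With the same 30% over-prediction across the top 5% (w = 0.706 and 0.745), the tenth reads 0.84 and 0.83.

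**Feasibility.** Section 6.8.9 states: "With over 35 million patients and at least 18,000 incident cases of oesophageal cancer on QResearch". A quarter of practices go to validation (section 6.2.1), so 18,000 / 4 = 4,500 cases. This is an upper figure: some cases are excluded or fall after 10 years. Splitting 64:31 by the two event rates (assumed) gives about 3,030 men and 1,470 women. The 95% interval for observed/expected is roughly ±1.96/√cases. Over a wider assumed range of C, 0.75 to 0.90:

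| Group | Men: cases | Men: interval | Women: cases | Women: interval |
|---|---|---|---|---|
| Top 5% | 740-1,720 | ±5-7% | 360-830 | ±7-10% |
| Top 1% | 260-920 | ±7-12% | 125-450 | ±9-18% |

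A true ratio of 0.77 in the top 1% would be detectable in either sex.

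**The case against.** A reader might infer that any usable cut-off must lie inside the top tenth. The protocol does not support this. Section 6.8.8 fixes no threshold, and rarity alone does not set one. With C of 0.75 to 0.90, the top tenth captures about 37-69% of cases and the top fifth about 54-83%, so a lower cut-off is plausible. Section 4.1 puts heartburn at 5-20% of the population.

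A reader might also infer that calibration by tenths cannot see error among those selected. That is too strong. Under the model above, a true log-risk slope half the predicted one within the top tenth can give 1.00 for the tenth but 0.57-0.61 in the top 1%. This works only if true risk jumps to 1.5-1.7 times predicted exactly at the 90th centile. If the slope halves continuously from that point, the tenth reads 0.59-0.66, which nobody would miss. The analyses by age band and in long-term PPI users also cut the high-risk population more finely and would show part of a masked error, although they are not aligned to the thresholds.

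Two further points have weight. Selection by centile depends on rank, as section 6.8.7 notes, and needs no calibration. And a statistical analysis plan, not at hand, may add curves or slopes. The first limits where the point applies. The second does not remove it, because the protocol itself chose the grouping and the one measure reported at each threshold.

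**Conclusion.** The point holds in conditional form. For any threshold above the 90th centile, the stated calibration check does not directly test absolute risk in the selected group, and an error concentrated in the extreme tail can be diluted to a few per cent or cancelled. The example, 0.77 in the top 1% becoming 0.92-0.94 in the top tenth, rests on an assumed lognormal spread, C of about 0.81-0.86 and the protocol's male event rate. It shows what the check could pass over and does not predict the model's error. This is a worthwhile improvement to the validation plan. It does not invalidate the tenths, the discrimination measures or the centile ranking.

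**What to change.** Keep the tenths. In sections 6.8.6 and 6.8.8, add for men and women separately:

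- mean predicted and observed 10-year risk, and observed/expected with a 95% confidence interval, above each centile threshold for which sensitivity is reported;
- a smoothed calibration curve with the upper tail legible;
- a calibration slope.

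The choice of centiles and bins stays with the sponsor. No new data are needed: the cost is a little more analysis, some extra table rows and one figure per sex. Intervals will be wider in the most extreme groups, especially for women, and should be shown so that sparse groups are not over-read.

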2.4 Vision

To re-design and evaluate the clinical pathway such that we systematically identify those at risk, perform a simple test to inform who needs endoscopy and in so doing rationalise the use of long-term PPI medication. Due to the cost-effectiveness of Cytosponge-TFF3 compared with endoscopy these changes will likely result in an economic benefit to the NHS, a social benefit for early detection of a lethal cancer and a reduction in over-use of PPI medication.

3 Summary Work Package 1

- **Objective** To derive and evaluate a risk prediction tool to predict oesophageal cancer (all types and according to squamous or adenocarcinoma subtype) which can be applied in primary care to identify high risk patients suitable for assessment with the Cytosponge in primary care.
- Design Prospective population based open cohort study using routinely collected data from 1500 GP practices in England in the QResearch database (derived from EMIS electronic medical records) between 01.01.2000 and 31.12.2020 (or latest data available). We will use the QResearch database to develop the risk equations. Models will be developed on a derivation dataset from a subset of approximately 1100 practices and validated in the remaining 400 practices. The model will be externally evaluated in other relevant datasets as they become available.
- Subjects We will study adults aged 40 years and over who are free of oesophageal cancer at study entry. Patients with a new onset of alarm symptoms (e.g. dysphagia, weight loss etc) in the preceding 3 months will also be excluded.
- Methods Cox time-to-event models will be used in the derivation data to derive separate risk equations in males and females for estimating risk of oesophageal cancer. Predictors considered will include age, ethnicity, deprivation, smoking status, alcohol intake, body mass index, pre-existing medical co-morbidities, and concurrent medication. Measures of performance (prediction errors, calibration and discrimination) will be determined in the validation data for men and women separately and by ten-year age group.
- **Outcome** Our primary outcome is oesophageal cancer defined as recorded on GP record or linked hospital, cancer registry or death certificate.

4 Background

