6.2.2 Patient inclusion

We will identify an open cohort of individuals aged 25-90 years who are registered with practices that have been contributing to QResearch for over 12 months on or after 1st January 2000 (study start date).

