6.3 Study period

Patients will enter the cohort on the latest of the study start date or the date on which they become 25 or 12 months after registering with their GP practice. Patients will be followed up until they develop oesophageal cancer, die, leave the practice or the study end date or a maximum follow up period of 15 years.

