6.8.5 Risk equations

We will use the regression coefficients for each variable from the final model as weights which we will combine with the baseline survivor function evaluated for each year up to 10 years to derive risk equations over a period of 10 years of follow-up⁴¹. This will enable us to derive risk estimates for each year of follow-up, with a specific focus on 10-year risk estimates. We will estimate the baseline survivor function based on zero values of centred continuous variables, with all binary predictor values set to zero.

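### Predicted and observed 10-year risk both ignore death as a competing event, so risk is overstated in older patients and the planned calibration cannot show that excess

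*Protocol*

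**What the plan says.** Four parts of the protocol together fix the method.

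- **Follow-up (6.3).** "Patients will be followed up until they develop oesophageal cancer, die, leave the practice or the study end date", with a maximum of 15 years. Death has the same role as leaving the practice. Under 6.4, oesophageal cancer on a mortality record counts as an event, so the deaths at issue are those without recorded oesophageal cancer.
- **Model (section 3, Methods).** "Cox time-to-event models will be used in the derivation data to derive separate risk equations", separately for men and women.
- **Risk equation (6.8.5).** The coefficients are weights to "combine with the baseline survivor function evaluated for each year up to 10 years to derive risk equations", "with a specific focus on 10-year risk estimates".
- **Calibration (6.8.6).** Patients are split into tenths by their predicted risk, and in each tenth the average prediction is set against an observed figure. On the source of that figure the section says: "The observed risks will be obtained using Kaplan-Meier estimates evaluated at 10 years, obtained for men and women". Performance is also evaluated by age group, including 70-79 and 80+, and in long-term PPI users.

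The protocol nowhere mentions competing risks, cumulative incidence or a net-risk target, and the limitations in 6.9.2 do not list the issue. The age range is not consistent: 6.2.2 has an "open cohort of individuals aged 25-90 years", the table shells in section 7 say 25-84 years, and the summary in section 3 says 40 and over.

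**The concern.** With death handled as an ordinary end of follow-up, one minus the survivor function is the probability of diagnosis in a hypothetical population where no other cause of death operates. One minus Kaplan-Meier estimates the same quantity. The proportion actually diagnosed within 10 years is lower, because people who die first cannot be diagnosed later. The gap grows with other-cause mortality, and so with age.

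This matters because absolute risk is part of the product. Section 5 foresees sharing results with patients, recalling patients by level of risk, mathematical modelling of the pathway and public web tools. Section 6.9.4 foresees displays of absolute risk, and says users will be told that the figures are in essence what was seen in the records of people with the same risk factors. A net risk does not fit that description in the oldest patients.

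The protocol names the estimators on both sides of the comparison, so this is not a detail left open for the analysis plan.

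**Working it through.** The protocol gives no figure for this effect, so there is none to reproduce. Its only usable input is the event rate for men in 6.8.9: 349 events / 543,952 person-years = 0.00064 per person-year. Death rates are not given; all those below are assumptions.

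**Step 1. Constant hazards, using the protocol's rate.** Let c be the cancer hazard and d the hazard of death without oesophageal cancer.

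- Planned quantity: 1 − exp(−10c). With c = 0.00064 this is 0.638%, whatever d is.
- Proportion actually diagnosed: c/(c+d) × [1 − exp(−10(c+d))].

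| Assumed d per year | Actually diagnosed by 10 years | Planned / actual |
|---|---|---|
| 0.5% | 0.622% | 1.03 |
| 1% | 0.607% | 1.05 |
| 2% | 0.578% | 1.10 |
| 4% | 0.526% | 1.21 |
| 6% | 0.480% | 1.33 |
| 10% | 0.403% | 1.58 |

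With the rate for women in 6.8.9 (0.00031) the ratios are practically the same.

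**Step 2. Would the planned check show it?** A simulation with c = 0.00064 used 2 million people in each of a derivation and a validation half.

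| Assumed d per year | Predicted / Kaplan-Meier | Predicted / actual proportion |
|---|---|---|
| 0.5% | 1.02 | 1.04 |
| 2% | 1.02 | 1.12 |
| 6% | 1.01 | 1.34 |
| 10% | 0.98 | 1.55 |

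The actual proportions of 0.620% and 0.407% at the two ends mean about 12,400 and 8,140 events per half. The standard error of a ratio is then about √(2/12,400) = 1.3% to √(2/8,140) = 1.6%, so the first column is compatible with 1 throughout. Each row stands for a group with its own death rate, so repeating Kaplan-Meier calibration by age group gives the same false reassurance on this component.

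**Step 3. Size by entry age.** Assumptions: mortality m = 0.008 per year at age 60 (range 0.006 to 0.010), doubling every 7.5 years; cancer hazard c = 0.001 per year. Net risk is 1 − exp(−0.01) = 0.995%. The cumulative incidence is the integral over 0 to 10 years of c × exp(−ct − M(t)), where M is cumulative mortality from entry.

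| Entry age | Cumulative incidence | Net / cumulative incidence (range over m) | Excess, percentage points |
|---|---|---|---|
| 60 | 0.942% | 1.06 (1.04-1.07) | 0.05 |
| 70 | 0.869% | 1.15 (1.11-1.18) | 0.13 |
| 80 | 0.718% | 1.39 (1.28-1.49) | 0.28 |
| 84 | 0.632% | 1.58 (1.42-1.74) | 0.36 |

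The ratio hardly depends on c, but the excess in percentage points scales with it. The range varies only the mortality level; the doubling time is also an assumption.

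**Step 4. Ranking.** On the same mortality, a 65-year-old with c = 0.0010 has net risk 1.00% and cumulative incidence 0.91%. An 84-year-old with c = 0.0013 has 1.29% and 0.82%. The order reverses, so ranks can change. To gauge how much, net risk and cumulative incidence were compared on assumed populations: cancer hazard rising 6-8% per year of age, log-normal other risk with SD 0.5-0.8, ages 25-90 or 40-84. Rank correlation was at least 0.996. Membership of the top 5% or 10% changed by 7-19%, but sensitivity changed by less than 1 percentage point.

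**The case against.** The best defence is that net risk is a legitimate target, that the protocol updates an existing family of tools with broadly the same methods (section 5 and 6.9.1), and that patients are to be grouped by centile with no absolute threshold (6.8.8), with rank order offered as sufficient if baseline survival drifts (6.8.7). In absolute terms the excess is also small below about age 70. All of this limits the impact. It does not answer the point, because the protocol never declares net risk as its target, and 6.9.4 tells users something closer to the opposite.

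Four stronger readings are tempting, and the documents do not support them.

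- **That calibration would look good whatever happens.** Kaplan-Meier by tenth of risk and by age group can still show overfitting, non-proportional hazards, imputation problems or differences between practices. Only the competing-death component is hidden.
- **That the centile thresholds are seriously distorted.** Step 4 shows some movement at the margin and little loss of sensitivity.
- **That risk is doubled in the oldest.** At entry age 90 the central ratio would be 2.07, but that age is in scope only under 6.2.2. The table shells stop at 84.
- **That the other histological subtype needs its own competing-event model.** With c = 0.001 and the other subtype at 0.00064 per year, the formula in step 1 gives a ratio of 1.003, which is negligible.

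**Conclusion.** The point holds for absolute risk. As written, the 10-year equation and its Kaplan-Meier comparator both estimate net risk, and the planned calibration, overall or by age group, cannot reveal the excess over the proportion actually diagnosed.

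The protocol does not use the word censoring. That reading follows from the end-of-follow-up rule, the Cox model and the survivor-function formula, with no competing-risk method named. The direction of the bias does not depend on any assumed figure, but its size rests on the assumed mortality in step 3. On that basis it is minor at 60, noticeable at 70 and material from about 80, the age group that 6.8.6 itself singles out. Figures above 84 apply only if the 25-90 range prevails. The consequence for selecting patients by centile is probably small.

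**What to change.** **In 6.8.6,** obtain observed 10-year risk from the Aalen-Johansen cumulative incidence, with death without oesophageal cancer as a competing event, by sex, tenth of predicted risk and age group. Kaplan-Meier may be shown beside it. This costs only wording and standard software commands, and it exposes the gap whichever risk equation is kept.

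**In 6.8.5,** compute the absolute risk that will be communicated or used in modelling as a cumulative incidence. Either combine cause-specific Cox models for oesophageal cancer and for death without it, or use a Fine-Gray model. If the net-risk equation is kept, label it as net risk wherever it is shown and report the gap from the cumulative incidence by age group.

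**Age range.** Reconcile 25-90, 25-84 and 40 and over, since the range determines how large the problem is.

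**Cost.** The cause-specific route needs a second fitted model per sex in the algorithm, with its own linear predictor and baseline hazard, plus integration over time; one more baseline function is not enough. Stated risks in the oldest patients will be lower. No separate competing model for the other histological subtype is needed.
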